4.1.1 Dose Escalation

The DLT assessment period is 21 days starting from the first dose of FN-1501. The study will follow a standard 3+3 dose escalation scheme and a modified Fibonacci sequence until the MTD is reached. Increments of 33% in the dose of FN-1501 will be undertaken after reaching 30 mg/day. Because of the dosage form (10 mg/vial), each dose will be rounded to numbers such as 2.5, 5, 10, 15, 22.5 mg/day, etc. At least three (3) patients will be enrolled into each cohort.

Additional patient(s), up to a maximum of four (4) patients in total, may be enrolled in a cohort if more than three (3) have been screened and are eligible for the cohort.

The DLT assessment and dose-escalation scheme will follow the same principle as stipulated for a standard 3+3 dose escalation design. For example, one (1) to three (3) additional patients will be enrolled if a DLT is observed in one (1) of first three (3) patients. No additional patients are required if a DLT is observed in one (1) of six (6) patients.

The starting dose will be 2.5 mg/day administered on the assigned days. One possible dose escalation scheme is presented in Table 1. Other dose levels may be evaluated during the study, depending on emerging data.

August 21, 2019 Confidential 32 / 74

Table 1: Suggested Dose Escalation Scheme

Dose Level/Cohort	Dose (mg/d)	Increase (%)
1	2.5	100
2	5	100
3	10	50
4	15	50
5	22.5	33
6	30*	33
7	40*	33

The actual dose levels and dose regimens administered in each step will depend on the data available from the previous level, as determined by the Safety Monitoring Committee.

As currently planned, if none (0) of the patients in one cohort experience DLT during the DLT assessment period, the dose to be administered in the next cohort will be increased by up to 100% (up to the 10 mg/d dose), by up to 50% (for the 10 mg and 22.5 mg doses) and by 33% thereafter, as determined by the SMC formed by the medical monitor, investigator, and sponsor representative.

The dose intervals will follow standard 3+3 escalation rules starting with the treatment of 3 patients as follows:

- 1. If 0 of 3 patients experiences a DLT, dose escalation will proceed to the next higher dose level at which 3 patients (up to 4) will be enrolled.
- 2. If 1 of 3 patients experiences a DLT, 3 more patients will be enrolled at the same dose level.
- 3. Escalation will continue if 0 or 1 of 6 patients experiences a DLT.
- 4. If 2 or more patients in any dose level experience a DLT, dosing will stop.

No additional patients will be treated at a given dose level if two (2) or more of the patients in the cohort develop a DLT during the DLT assessment period. In this instance, the MTD is considered to have been exceeded. If the MTD is exceeded, the next lower dose level is considered MTD. Depending on the decision of the SMC and on review of available data, an additional intermediate

August 21, 2019 Confidential 33 / 74

^{*} Increments of 33% in the dose of FN-1501 will be undertaken after reaching 30 mg/day until the MTD is reached.

dose level, between the MTD-exceeding dose level and the next lower dose level, may be explored. If an MTD is not identified due to paucity of DLTs, the RP2D will be determined based on PKs, safety, tolerability, and preliminary efficacy.

DLT Definition:

DLT is any AE not attributable to disease or disease-related processes that occur during the DLT assessment period. DLT is determined by investigators based on NCI-CTCAE Version 4.03:

Non-hematologic:

- Grade 3 or greater nausea, vomiting and diarrhea despite optimal supportive care
- Any other clinically relevant ≥ Grade 3 non-hematologic toxicity (excluding asymptomatic biochemical abnormalities that are not clinically significant and resolve to Grade 2 or less in <7 days)
- Persistent Grade 2 toxicity such as nausea, vomiting, or fatigue despite optimal standard medical therapy that, in the opinion of the investigator, prevents continuous dosing
- Any toxicity which in the judgment of the investigator or sponsor is dose limiting

Hematologic:

- Grade 4 neutropenia lasting > 7 days
- Grade 3 Febrile neutropenia (defined as absolute neutrophil count [ANC] < 1000/mm³ with a single temperature of 38.3°C or a sustained temperature of 38°C for > 1 hour)
- Grade 3 neutropenic infection
- Grade 3 thrombocytopenia with bleeding
- Grade 4 thrombocytopenia

For elevations in hepatic function enzymes, DLT is defined as follows:

- Grade 4 aspartate aminotransferase (AST) or alanine aminotransferase (ALT) increase
- AST or ALT > 5 × upper limit of normal (ULN) if accompanied by ≥ Grade 2 elevation in bilirubin
- AST or ALT > 5 × ULN lasting > 3 days in patients without liver metastases

August 21, 2019 Confidential 34 / 74

• AST or ALT > 5 × ULN lasting > 3 days if the baseline value was ≤ 3 × ULN in patients with liver metastases

• AST or ALT > 8 × ULN lasting > 3 days if the baseline value was > 3 × ULN but ≤ 5 × ULN in patients with liver metastases

Specific DLT definitions for patients with AML:

Non-hematologic:

• All non-hematologic toxicities NCI-CTCAE ≥ Grade 3

Hematologic:

Prolonged myelosuppression defined as persistence of ≥ Grade 4
neutropenia or thrombocytopenia in the absence of leukemia (blast count
<5%) at least 42 days after the initiation of Cycle 1

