PROTOCOL AMENDMENT, VERSION 3

Amendment rationale

Protocol FN-1501-UP1 is updated:

To include patients with relapsed/refractory Acute Myelocytic Leukemia
 (AML)

Rationale in Acute Myeloid Leukemia:

Patients with AML have a clear need for new therapeutic options. Preclinical data from in vivo studies suggest that FN-1501 as a single agent could offer cancer patients clinical benefit by inhibiting multiple tyrosine kinases including FMS-like tyrosine kinase 3 (FLT3), mutations of which are associated with leukemic transformation, and are present in up to 30% of this patient population.

Considering that AML is not an ideal for a first in human study due to its rapid natural history and the risk of under-dosing the patients leading to rapid progression, the first in human study of FN-1501 only included patients with histologically or cytologically confirmed advanced solid tumors. Currently, this ongoing clinical trial has treated 9evaluable patients with solid tumors that completed the dose limiting toxicity (DLT) period in three cohorts of ascending doses, including 2.5 mg, 5.0 mg, and 10 mg. Cohort 4 at 15 mg is on-going. No DLTs have been reported.

As the ongoing study is approaching the expected efficacious range for FN-1501, which has been estimated at 15-30 mg daily (based on preclinical data), we are amending the protocol to include the target patient population (AML) in the Study FN1501-001. Patients with AML that have no standard therapeutic options enrolled in this clinical trial will not be treated at subtherapeutic doses and patients may receive clinical benefit since an active dose is expected.

- o To modify the life expectancy of enrolled patients to at least three months
- To modify dose escalation rules. Increases of doses of FN-1501 will be set at 33% after 30 mg/day dose to have a traditional escalation scheme with meaningful change (currently the dose escalation is 16%) until the maximum tolerated dose (MTD) is reached

August 21, 2019 Confidential 5 / 74

o To include a pharmacokinetic (PK) sample at steady state on Day 1 of Cycle 2

- To add DLT definitions for patients with AML
- o To include evaluation criteria for patients with AML
- To modify the frequency of evaluation criteria for patients with solid tumors to every 6 weeks to align with the study-drug treatment schedule
- To include bone marrow biopsy in patients with AML
- o To clarify electrocardiogram (ECG) procedures

August 21, 2019 Confidential 6 / 74

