4.1 Summary of Study Design

This is a phase 1, first-in-human, open-label, multi-center, single-arm, dose escalation clinical study in patients with histologically or cytologically confirmed advanced solid tumors or relapsed/refractory AML, who cannot tolerate or do not respond to standard systemic therapy.

Patients will be screened for eligibility for up to 21 days prior to entry into the study. The starting dose will be 2.5 mg/day on the assigned days. Dose escalation will use the traditional 3+3 design and follow a modified Fibonacci sequence until MTD is reached. Increments of 33% in the dose of FN-1501 will be undertaken after reaching 30 mg/day. Eligible patients will receive a single intravenous infusion of study drug on Days 1, 3, 5, 8, 10, and 12 of a 21-day cycle.

The DLT assessment period is 21 days from the first dose of FN-1501. Evaluation of a cohort of at least three (3) patients completing DLT assessment at any given dose level is required prior to determining the next dose level and dose regimen for the subsequent cohort.

August 21, 2019 Confidential 31 / 74

The highest dose under which one or no case of DLT is observed will be considered as MTD. If DLT cannot be observed, RP2D will be determined based on safety, preliminary anti-tumor activities and PK data.

Approximately thirty-three patients are expected to be enrolled.

After the first patient in the cohort receives the Cycle 1, Day 1 dose, subsequent patients in that cohort will not be dosed until the first patient has been evaluated for at least 48 hours to exclude unexpected acute toxicity. The continuous safety evaluation will be performed by investigators, the medical monitor, and the sponsor. A Safety Monitoring Committee (SMC) will determine dose levels to be administered and dose regimen during dose escalation based on the data available from the previous dose levels. If an MTD is not identified due to paucity of DLTs, the RP2D will be determined based on PKs, safety, tolerability, and preliminary efficacy.

If a patient wishes to continuously receive study treatment on completion of Cycle 1, the patient can continue study treatment in 21-day Cycle 2 and subsequent cycles (same as Cycle 2, all of 21 days' duration), defined as administration of 3 times per week for 2 weeks followed by 1 week rest, at the discretion of the investigator.

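### Section 4.1.1 is inconsistent on expansion after one DLT: one to three more patients or exactly three, a cap of four against rules that need six, and no stated action for one DLT in four.

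*Protocol*

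**What the plan says.** All of the rules at issue are in the protocol, mostly in Section 4.1.1 (Dose Escalation).

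- **Cohort size.** At least three patients per cohort. If more than three are screened and eligible, additional patients, "up to a maximum of four (4) patients in total, may be enrolled in a cohort". Rule 1 repeats this for the next level: "dose escalation will proceed to the next higher dose level at which 3 patients (up to 4) will be enrolled".
- **No DLT.** Rule 1 escalates on 0 of 3. A separate sentence escalates when nobody in the cohort has a DLT, which covers 0 of 4.
- **One DLT, worked example.** "one (1) to three (3) additional patients will be enrolled if a DLT is observed in one (1) of first three (3) patients".
- **One DLT, rule 2.** "If 1 of 3 patients experiences a DLT, 3 more patients will be enrolled at the same dose level".
- **After expansion, rule 3.** "Escalation will continue if 0 or 1 of 6 patients experiences a DLT".
- **Two or more DLTs.** Rule 4 stops dosing, and the paragraph after it says: "No additional patients will be treated at a given dose level if two (2) or more of the patients in the cohort develop a DLT".
- **MTD (Section 4.1, and in substance in Section 3.1 and the Synopsis).** "The highest dose under which one or no case of DLT is observed will be considered as MTD".
- **Sample size (Section 10.1).** Seven cohorts, with six patients in the fourth and later cohorts, give about 33 patients.

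**The concern.** The three statements about how many patients follow a single DLT do not fit together. One sentence allows one, two or three more patients, while rule 2 requires three. The cap of four in total is not limited to initial enrolment, and the Amendment 4 rationale also describes it as the maximum per cohort. Taken at its word, it would prevent a cohort from reaching the six on which rules 2 and 3 depend.

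Following the text can therefore leave a dose level at 1 of 4 or 1 of 5. No escalation rule applies to either result, yet both meet an MTD definition that counts DLTs without saying among how many patients. These are the operating rules of a first-in-human escalation. They decide who is exposed to the next dose, and they produce the MTD, which is part of the primary endpoint. Sites and the Safety Monitoring Committee apply them in real time, so they have to be settled in the protocol.

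**Working it through.** **1. The plan's own figure.** Section 10.1: 3 cohorts × 3 + 4 cohorts × 6 = 9 + 24 = 33. It reproduces.

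**2. Outcomes of a four-patient cohort against the text.**

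| DLTs in four | Stated action |
|---|---|
| 0 | Escalate (no DLT in the cohort) |
| 1 | None |
| 2 or more | Stop (rule 4 and the paragraph after it) |

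Under the one-to-three wording, 1 of 3 can also become 1 of 4 or 1 of 5. Neither has a rule.

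**3. How often it arises, and what the readings do.** The protocol gives no DLT rates, so the rates *p* below are assumptions; *q* = 1 − *p*.

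- Exactly 1 of 4: 4*pq*³.
- DLT in the fourth patient only: *pq*³, one quarter of the line above. This is the unruled case if the rules are read as keyed to the first three patients.
- Escalate, standard 3+3: *q*³ + 3*pq*²·*q*³.
- Escalate, 1 of 4 filled to six: *q*⁴ + 4*pq*³·*q*².
- Escalate, 1 of 4 accepted: *q*⁴ + 4*pq*³. This equals *q*³(1 + 3*p*), the result of adding one patient to 1 of 3 and escalating if that patient has no DLT.
- Escalate, two patients added to 1 of 3, no further DLT: *q*³ + 3*pq*²·*q*².

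| Assumed true DLT rate | 10% | 20% | 33% | 40% |
|---|---|---|---|---|
| Exactly 1 of 4 | 0.292 | 0.410 | 0.397 | 0.346 |
| DLT in fourth patient only | 0.073 | 0.102 | 0.099 | 0.086 |
| Escalate: standard 3+3 | 0.906 | 0.709 | 0.434 | 0.309 |
| Escalate: 1 of 4 filled to six | 0.892 | 0.672 | 0.380 | 0.254 |
| Escalate: 1 of 3 plus two | 0.926 | 0.758 | 0.500 | 0.372 |
| Escalate: 1 of 4 accepted, or 1 of 3 plus one | 0.948 | 0.819 | 0.599 | 0.475 |

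At 33%: *q*³ = 0.3008, *q*⁴ = 0.2015, *q*⁵ = 0.1350. Standard 3+3: 0.3008 + 0.99 × 0.1350 = 0.434. Accepting 1 of 4: 0.2015 + 1.32 × 0.3008 = 0.599. Between the tabulated rates, the chance of 1 of 4 peaks at 0.422 when *p* = 25%.

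**4. Cost of filling to six.** Two more patients when 1 of 4 occurs. The mean per four-patient cohort is at most 2 × P(1 of 4) = 0.58, 0.82, 0.79 and 0.69 at the four rates.

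**The case against.** The strongest reply is that the text, read as a whole, already points to six. Escalation is stated on only two grounds, no DLT in the cohort or at most 1 of 6, and 1 of 4 meets neither. The section says that it follows the principle of a standard 3+3, and Section 10.1 plans six per cohort once DLTs occur. The one-to-three sentence is introduced as an example, and it can be squared with rule 2 if enrolment stops at a second DLT. The cap is tied to having more than three eligible patients, so it most naturally concerns initial enrolment. The rules also speak of the first three patients. If they are keyed to those three, a DLT among them triggers rule 2, and only a DLT in the fourth patient alone is unruled.

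Much of this stands. It lowers the unruled case from 29% to 41% down to 7% to 10% at the tabulated rates. It also means that the 60% figure describes a misreading, not the stated plan. The fair comparator for that figure is the standard 3+3 at 43%; filling 1 of 4 to six gives 38%, but that is the repair proposed here.

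The reply does not remove the inconsistency. Each reconciliation is supplied by the reader: the text does not link rule 2 to the second-DLT stop, does not limit the cap to initial enrolment, and does not say whether a fourth patient already treated counts among rule 2's three. If that patient does not count, 1 of 4 leads to seven.

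**Conclusion.** Section 4.1.1 is wrong as written on expansion after one DLT, and should be corrected. The two expansion sizes and the literal cap conflict, and 1 of 4 has no stated action. The MTD definition does not close the gap, because it names no denominator.

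The size depends on assumed DLT rates and on the cohort taking the optional fourth patient. One DLT in four has probability 29% to 41% at the tabulated rates; on the narrower first-three reading, the unruled case is 7% to 10%. If a committee did treat 1 of 4 as permission to escalate, the chance of escalating would be 60% rather than 43% at a 33% rate, and 48% rather than 31% at 40%.

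A reader might infer that the protocol permits escalation on 1 of 4. It does not say so, and its stated grounds for escalating point the other way. Nor is the sample size in error: 33 reproduces. But 33 is an approximate size, not a ceiling, because Section 4.1.1 allows intermediate and other dose levels, and Sections 4.2.4.2, 5.4 and 10.2.3 provide for replacing patients. Nothing suggests that the completed levels were affected: the Version 3 rationale reports that the trial "has treated 9evaluable patients with solid tumors that completed the dose limiting toxicity (DLT) period in three cohorts", with no DLTs reported.

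**What to change.** Make three changes of wording.

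1. Replace both expansion statements with one rule: if 1 of the first 3 or 4 patients has a DLT, enrol further patients to a total of six at that dose level, stopping if a second DLT occurs; after such an expansion, escalate only if at most 1 of 6 has a DLT. A cohort of three or four with no DLT escalates as now. Fixing the total at six, instead of a number to add, prevents a cohort of four from growing to seven.
2. State that the maximum of four applies to initial enrolment only.
3. State in Sections 3.1, 4.1 and the Synopsis that, where a DLT has occurred at a dose, that dose can be the MTD only with at most 1 DLT in six patients.

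The cost is at most two more patients in an affected four-patient cohort. That stays within the six per cohort that Section 10.1 already plans from level 4.

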4.1.3 Study Procedures

Study procedures are listed and described in Table 2. Detailed descriptions of the time points for PK sampling, ECG, and vital signs evaluations in the first week of Cycle 1 is included in Table 3.

August 21, 2019 Confidential 35 / 74

Table 2: Study Assessment and Procedure Schedule

Assessment	Screen period		Cycle 1 (21 days)						Subseq	uent 21 days)	Follow-up/ End of Study
Day of Cycle	-21 to	1 ¹	2	3	5	8	10	12	1 ² (±3)	8 (±3)	30 to 35 days post last dose
Inform consent	X										
Review eligibility	X										
Demographic data	X										
Medical history/ baseline conditions	X										
Disease assessment Solid Tumors ³	X		Every 6 weeks \pm 5 days and as detailed in the footnote								
Disease Assessment AML ³	X		Every 6 weeks \pm 5 days and as detailed in the footnote								
Vital signs	X	X^4	X	X ⁴	X ⁴	X^4	X^4	X^4	X^4	X ⁴	X
Weight	X	X^4	X	X ⁴	X ⁴	X^4	X^4	X ⁴	X^4	X ⁴	X
Physical exam ⁵	X	X^4	X	X ⁴	X^4	X^4	X^4	X ⁴	X ⁴	X ⁴	X
ECOG performance review	X	X ⁴				X ⁴			X^4		X
12-lead ECG ⁶	X	X							X		X
Concomitant medications review	X	X				X			X		X
CT or MRI (solid tumor only)	X ⁷	Every 6 weeks ± 5 days									
Pregnancy test ⁸	X	X							X		
Hematology ⁹	X	X ⁴				X^4			X ⁴	X^4	X
Blood chemistry + amylase and lipase tests ⁹	X	X^4				X ⁴			X ⁴	X^4	X

August 21, 2019 Confidential 36 / 74

Assessment	Screen period		Cycle 1 (21 days)						Subsequent cycles (21 days)		Follow-up/ End of Study
Day of Cycle	-21 to	1 ¹	2	3	5	8	10	12	1 ² (±3)	8 (±3)	30 to 35 days post last dose
Bone Marrow Biopsy for patients with AML ¹⁰	X			Every	6 wee	eks ± :	5 days	and as	detailed i	n the footn	ote
Coagulation test ⁹	X										X
Urinalysis ¹¹	X								X		X
Adverse event	X						Хс	ontinuo	ous		
PK blood sample		X	X	X ¹²					X ¹²		
Study drug ¹³ administration		X		X	X	X	X	X	X	X	

Abbreviations: AML = Acute Myeloid Leukemia; BMI = Body Mass Index; CT = computed tomography; ECOG = Eastern Cooperative Oncology Group; MRI = magnetic resonance imaging; PK = pharmacokinetic

- 1. On Day 1 of Cycle 1, patients may need to stay at the clinical research unit overnight to complete PK sampling, safety observation and assessments.
- 2. For DLT cycle, patients will return for the end of the DLT assessment period (21 days from first dose of FN-1501) assessments on Day 1 of Cycle 2 (± 3 days). If additional cycles are planned, patients will start Day 1 dosing of next cycle after the assessments. For the last cycle, patients will return for the assessments.

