- 3. Disease assessment every 6 weeks to coincide with every other cycle. Refer to Section 7.4 for details.
- 4. These assessments should be conducted, and the results should be available before study drug administration in each cycle. If assessments are conducted within 3 days prior to Day 1 of the cycle, the data can be recorded as Day 1 data of the cycle. See Table 3 for details. Height to be measured at Screening for BMI calculation.
- 5. A full physical exam will be conducted at screening, on Day 1 of each cycle and at follow-up. A full physical exam includes assessments of cardiovascular, respiratory, abdominal and neurological systems as well as lymph nodes/spleen, skin, oropharynx and extremities. Refer to Section 7.1.2 for details.

August 21, 2019 Confidential 37 / 74

6. ECGs to be performed prior to that days dose (if applicable) and after the patient has been supine for at least 10 minutes and should be performed with the patient in the same physical position for the duration of the test. ECG at Screening: performed in triplicate (5-10 min between readings). ECG at Day 1 of Cycle 1: performed in triplicate (5-10 min between readings) at the days indicated in Table 2 and time points and time windows detailed in Table 3. Cycle 2 Day 1: Perform in triplicate (5-10 min between readings) only if patient has a significant QTc prolongation, that is, a) > 500 msec; or b) increased by ≥ 60 msec over baseline; and/or c) decreased by 50 msec below pre-dose recording. If prolongation of QT or QT interval corrected for heart rate (QTc) is noted during the first 2 weeks, triplicate 12 lead ECGs will be conducted weekly during Cycle 2, and then once every 3 weeks before administration and 5-15 minutes after administration on Day 1 of every cycle from Cycle 3 onwards, until discontinuation of FN-1501 treatment. Refer to Section 7.1.3 for details on significant QTc prolongation.

- 7. Data obtained up to 42 days prior to Day 1 is acceptable.
- 8. Only in women of childbearing potential and additionally at the investigator's discretion.
- 9. In the event of neutropenia, thrombocytopenia, or \geq Grade 3 clinical chemistry toxicity, these assessments will be conducted as frequent as the investigator feels necessary until toxicity is resolved (\leq Grade 2). Refer to Table 6 for details on laboratory assessments.

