7.1 Assessments During the Treatment Period

Routine safety assessments include vital signs, weight, physical exam, and AE assessment will be performed at every visit. Other safety assessments include 12-lead ECG, bloodwork, disease assessments, bone marrow biopsy for related assessments for patients with AML, and urinalysis will be performed as indicated in Table 2.

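### No haematology or chemistry is required between Cycle 1 Day 8 and Cycle 2 Day 1, so silent laboratory DLTs that start after Day 8 are not reliably ascertained

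*Protocol*

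**What the plan says.** **DLT definitions (Protocol Section 4.1.1).** The DLT period is 21 days from the first dose. For solid tumours, several criteria can be met on laboratory values alone: "Grade 4 neutropenia lasting > 7 days", "Grade 4 thrombocytopenia" with no duration attached, Grade 4 AST or ALT, and "AST or ALT > 5 × ULN lasting > 3 days in patients without liver metastases", with variants for patients with liver metastases. For AML the non-haematologic criterion is "All non-hematologic toxicities NCI-CTCAE ≥ Grade 3", which has no duration requirement and so takes in chemistry values. The AML haematologic criterion is read "at least 42 days after the initiation of Cycle 1".

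**Laboratory schedule (Section 4.1.3, Table 2).** The haematology row and the row for "Blood chemistry + amylase and lipase tests" are marked in Cycle 1 on Days 1 and 8 only. The next mark is Day 1 of the following cycle (± 3 days), which footnote 2 makes the end-of-DLT assessment. Days 10 and 12 are dosing visits with vital signs, weight and physical examination but no blood tests. Table 2 has no visit between Day 12 and Cycle 2 Day 1.

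**Supporting text.** Section 7.1 puts only vital signs, weight, physical examination and AE review at every visit. Its sentence beginning "Other safety assessments include 12-lead ECG, bloodwork, disease assessments" refers those items back to Table 2. Footnote 9 adds tests once neutropenia, thrombocytopenia or a Grade 3 or higher chemistry toxicity is present: "these assessments will be conducted as frequent as the investigator feels necessary until toxicity is resolved". Section 7.1.1 adds discretionary testing. Footnote 4 requires results before dosing and lets values from up to 3 days earlier stand as Day 1 data.

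**The concern.** A criterion with a duration threshold needs enough draws to see the abnormality and to show how long it lasted. After Day 8 the protocol mandates none until the DLT period is nominally over. Because the Day 8 sample is taken before dosing, three of the six doses (Days 8, 10 and 12) and the whole rest week follow the last mandatory test.

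The count feeds straight into the 3+3 rules of Section 4.1.1. One missed DLT turns 1 of 3 into 0 of 3, so the trial escalates without expanding the cohort. It turns 2 of 6 into 1 of 6, so the trial continues where it should stop. Under-ascertainment can only lower the count, and the MTD is a primary endpoint of a first-in-human study. Section 1.3 lists decreased blood cell count as drug-related in both rats and monkeys, so cytopenia is a toxicity the schedule should be able to see.

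**Working it through.** The protocol gives no figure for this point. Its one design number, about 33 patients, follows from 3 × 3 + 4 × 6 = 33 (Section 10.1) and plays no part here.

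**Inputs.** DLT window Days 1–21 (Section 4.1.1). Doses on Days 1, 3, 5, 8, 10 and 12 (Section 4.1). Mandatory draws on Day 8 and on Day 22 ± 3 (Table 2, footnote 2). Early-draw allowance of 3 days (footnote 4).

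**Gap from the Day 8 draw.**
- Nominal: 22 − 8 = 14 days
- Visit window: 19 − 8 = 11 to 25 − 8 = 17 days
- Literal minimum, adding footnote 4 to a Day 19 visit: (19 − 3) − 8 = 8 days

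**Which episodes are sampled.** Count in whole days. An episode of d days with onset on day o is sampled if some draw day D satisfies o ≤ D ≤ o + d − 1, that is, if a draw falls while the value is at the qualifying level. It starts after Day 8 and completes in the window if o ≥ 9 and o + d − 1 ≤ 21.
- Shortest neutropenia DLT, more than 7 days: d = 8, so o = 9 to 14, 6 onset days.
- Shortest AST/ALT DLT, more than 3 days: d = 4, so o = 9 to 18, 10 onset days.

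Unsampled onset days among these:

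| Draws after Day 8 | d = 8 (of 6) | d = 4 (of 10) |
|---|---|---|
| Day 22 (nominal) | 6 | 10 |
| Day 25 | 6 | 10 |
| Day 19 | 3 | 7 |
| Day 16 (footnote 4 extreme) | 0 | 6 |
| Days 12 and 22 | 2 | 6 |

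The longest run that no draw touches is Days 9–21, 13 days, with a Day 22 draw. Adding Day 12 shortens it to Days 13–21, 9 days.

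If every onset from Day 9 to Day 21 is counted, whether or not the episode ends by Day 21, the Day 22 draw misses 6 of 13 onsets for d = 8 and 10 of 13 for d = 4.

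An earlier last draw sees more mid-window episodes but leaves the end of the window untested: Days 20–21 after a Day 19 draw, Days 17–21 after a Day 16 draw.

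**Direction of the effect (illustration only).** Under the 3+3 rules the chance of escalating is (1 − q)³ + 3q(1 − q)² × (1 − q)³, where q is the true DLT rate times the share of DLTs ascertained. Assume a true rate of 0.33. The chance is 0.43 if all DLTs are ascertained, 0.61 at 75%, 0.78 at 50% and 0.93 at 25%. The protocol gives no basis for choosing a share, so these values show direction and not an estimate.

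**The case against.** *The in-window count is true by construction.* Any episode confined to Days 9–21 must miss a Day 22 draw, and the DLT definition does not say that the duration has to finish by Day 21. That is fair, and the all-onset figure for an 8-day neutropenia is milder (6 of 13). It remains a large share, and for a 4-day AST/ALT rise it is 10 of 13.

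*The protocol allows extra tests.* Footnote 9 names neutropenia and thrombocytopenia without a grade, Section 7.1.1 permits further testing when warranted, and Sections 3.2 and 7.4 allow more frequent counts in AML. A falling count on Day 8 or a recovering one on Day 22 may therefore prompt draws. This narrows the gap in practice. But the tests are discretionary or follow an abnormality already found, and Section 7.1.1 sets its haematology triggers at ANC below 1000/mm³ and platelets below 50,000/mm³. The day counts show what the table fails to mandate, not what every site would miss.

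*Unknown duration does not rule out a DLT.* Section 4.1.1 lets the investigator or sponsor call any toxicity dose limiting, and the Safety Monitoring Committee reviews all available data. That helps with an abnormality found on Day 22 whose start is unknown. It cannot help with an episode that nobody sampled.

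*Day 19 dosing is not clearly allowed.* Section 4.1.2 places further treatment after the DLT period, and Section 4.1 after Cycle 1. Yet the ± 3-day column of Table 2 includes the study-drug row, and footnote 2 lets dosing follow the assessments. The passages conflict as they stand.

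**Conclusion.** The point holds. The protocol defines DLTs by laboratory grade and duration but mandates no haematology or chemistry for a nominal 14 days (11 to 17 with the visit window) of a 21-day DLT period. Silent laboratory DLTs with onset after Day 8 are not reliably ascertained: in solid tumours, Grade 4 neutropenia beyond 7 days, Grade 4 thrombocytopenia, and the AST/ALT criteria; in AML, Grade 3 or higher chemistry toxicity. A value still recovering near Day 22 may lead to more tests but cannot date the start of the episode.

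Not affected are the AML haematologic criterion, abnormalities already known on Day 8, and events that show themselves clinically.

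The day counts assume whole days and detection only at the qualifying level; they are not probabilities. The bias runs one way, towards escalation and a higher MTD. Its size depends on how many DLTs are silent and late, which the protocol does not give. Confidence is high for the schedule gap and its direction, not for any particular effect on the MTD.

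Separately, footnote 2 allows the end-of-DLT assessment, and then Cycle 2 dosing, on Day 19, before the 21-day period ends.

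**What to change.** Reconcile Table 2 with the DLT definitions so that laboratory sampling between Day 8 and the end of the window can detect the criteria of more than 3 and more than 7 days.

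- The cheapest step is a haematology and chemistry draw at the existing Day 12 visit. With a Day 22 end draw it samples 4 of the 6 in-window onsets of an 8-day neutropenia and 4 of the 10 of a 4-day AST/ALT rise.
- It does not close the gap alone. Onsets on Days 13–14 (8-day) and Days 13–18 (4-day) stay unsampled. Whether to add a draw in the rest week, and how closely to space repeat draws to establish duration, is for the sponsor to decide.
- Reconcile footnotes 2 and 4 with the 21-day window in Sections 4.1.1 and 4.1.2, so that the end-of-DLT laboratory assessment does not precede the end of the window.

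The cost is one or two extra local-laboratory draws per patient in Cycle 1, one of them at an existing visit, plus changes to the table and footnotes.
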